5.0 Study Intervention/Investigational Agent

5.1 [name] laboratory research coordinator, [name], who is the research coordinator for previous and ongoing tDCS studies (R01NR019051 and R15NR018050), will be responsible for coordinating and supervising the intervention sessions. Equipment will also be provided by [name] lab. Participants will receive a brief training at the lab to explain the procedure and how to use the device at the time of enrollment (after their preoperative visit at the clinic). Participants will go home with the tDCS device and videoconference meetings will be scheduled for the monitoring of sessions. Each session will start with tDCS and end with a brief mindfulness meditation using audio recording, i.e., 3-minute breathing space. This exercise is a well-established strategy that is being used in MBI for acute pain¹⁹ and chronic pain³⁵.

6.0 Procedures Involved*

6.1 This study will use double-blind randomized sham-controlled design with an allocation ratio of 1:1 with repeated measures at 4 time points. Participants will be randomly assigned to one of 2 arms as follows: 1) preoperative active tDCS+MBI or 2) preoperative sham tDCS+MBI. Participants will be recruited at their preoperative visit (see letter of collaboration). A clinician (registered nurse or surgeon) or a research coordinator from the clinic will review the preoperative

PROTOCOL TITLE:

clinic schedule, conduct a pre-screening of potentially eligible participants, and introduce the study to potential participants at their preoperative visit by using a flyer. If the individual agrees to learn more, the PI or RA ([name]) will enter the room to discuss study, answer questions and sign the consent. If they agree to participate, after signing the consent, they will be invited to come to the brain stimulation laboratory (FSU innovation park) where a baseline assessment will be done before randomization by the RA or lab research coordinator ([name]). The tDCS device along with instructions will then be provided. The baseline visit will take approximately 2 hours. The preop procedures will be as follows with T = day of surgery:

T-7: Recruitment/Consent

T-6: Baseline lab measurements & tDCS fitting and training

T-5: AM & PM remote tDCS/MBI

T-4: AM & PM remote tDCS/MBI

T-3: AM remote tDCS/MBI + Post-intervention lab measurement & collect tDCS equipment

6.2 Measures:

Usual sociodemographic variables (i.e., age, sex, civil status, living conditions, education level, and employment status) will be assessed. Relevant medico-surgical information during hospitalization will be collected: type of surgery, postoperative complications, and current involvement in a rehabilitation program. The presence of chronic pain before surgery will also be documented.

Outcome measures will be taken at 4 time points: 1) baseline (before preoperative active/sham tDCS+MBI), 2) after 5 sessions of preoperative active/sham tDCS+MBI, 3) after surgery, and 4) 1 month after surgery. Table 1 gives an overview of all measures for the preoperative and postoperative phases.

Analgesic consumption. The dose of every opioid received within 5 days postoperatively will be transcribed and converted into standardized parenteral morphine equivalents using the Centers for Disease and Control Prevention Guidelines on opioids ⁴². A total in milligrams will be calculated for each day and means will be obtained for all groups.

Pain severity. Pain intensity is a global indicator of the pain experience. It will be assessed with a numerical rating scale (NRS) (0-100) with the anchors being no pain at all (0) and worst possible pain (100). This type of scale is recognized for its reliability, validity and sensitivity in various clienteles and settings ^{41,43,44} and is a reliable and well-validated measure with good ability to detect pain change in adults with knee OA ⁴⁵. Four different measures of pain intensity will be taken: 1) average pain upon movement in the past 7 days, 2) worst pain upon movement in the past 7 days, 3) present pain upon movement, and 4) present pain at rest. As suggested by the IMMPACT group in regard to pain core domains in clinical trials ^{41,46}, the impact of pain on various aspects of daily living will be assessed with interference items of the Brief Pain Inventory (BPI) ⁴⁷. The BPI has been successfully validated patients suffering from OA and undergoing TKR ^{6,48}. It includes seven items and evaluates the impact of pain on general activity, mood, walking, work, relationships, sleep, and enjoyment of life via a NRS (0-10). Each item represents a subscale and can be scored and analyzed individually (0-10), with the anchors being “does not interfere” (0) and “completely interferes” (10). A total interference score can also be calculated by taking the sum of all the items. Additionally,

PROTOCOL TITLE:

with regards to emotional function, considering established relations between pain, anxiety, and depression⁴⁹, measures of anxiety and depression will be taken with the *Patient Health Questionnaire-4 (PHQ-4) for depression and anxiety* at all time points⁵⁰. Total score is determined by adding together the scores of each of the 4 items. Scores are rated as normal (0-2), mild (3-5), moderate (6-8), and severe (9-12). Total score ≥ 3 for first 2 questions suggests anxiety. Total score ≥ 3 for last 2 questions suggests depression. The validity and reliability of the Patient Health Questionnaire-4 has been well established including with surgical clientele^{51,52}. The *Pain Catastrophizing Scale*⁵³ will be used to assess patients' pain-related catastrophic thoughts. It includes 13 items divided into three subscales: rumination (4 items), magnification (3 items), and helplessness (6 items). Each item is rated on a 5-point scale with the end points not at all (score=0) and all the time (score=4). The total score and scores for each subscale can be calculated by taking the sum of the items. The Pain Catastrophizing Scale has demonstrated an excellent internal consistency, and its sensitivity in the context of chronic pain has been established^{54,55}. Pain severity will also be measured 1 month after surgery to explore sustained efficacy of combined tDCS+MBI on the incidence and severity of persistent post-surgical pain.

A multimodal Quantitative Sensory Testing (QST) battery will be completed: heat pain (e.g., threshold, tolerance), pressure pain threshold, punctate mechanical pain (e.g., suprathreshold ratings and temporal summation), and Conditioned Pain Modulation (CPM). These measures, which were utilized in our previous and ongoing study (R01NR019051 and R15NR018050), will be assessed using equipment and methods available at the [name] laboratory, including a Medoc TSA-II Neurosensory Analyzer and Wagner pressure algometer.

Acceptability and feasibility. We will collect data on participants' tDCS experience via a questionnaire, at the conclusion of tDCS treatment on a 0 (strongly disagree) to 10 (strongly agree) scale: 1) It was easy to prepare the device and accessories; 2) The device was unnecessarily complex; 3) The device was easy to use; 4) I felt the video conferences with a technical person were helpful; 5) I would imagine that most people would learn to use this device quickly; 6) The device was cumbersome to use; 7) I felt confident using the device; 8) I needed to learn a lot of things before I could get going with this device; 9) The effectiveness of the treatment increased over the course of treatment; 10) Overall, I felt that transcranial electrical stimulation treatment benefited me. Moreover, we will evaluate the presence and severity of possible side effects of treatment at the end of each session on a 0 (not at all) to 10 (highest degree) scale. By using open-ended questions, the participants will be asked whether they experienced any side effects, and they will then be asked specifically about tingling, itching sensation, burning sensation, pain at the stimulation site, fatigue, nervousness, headache, difficulty concentrating, mood change, and changes in vision or visual perception. If any side effects are reported, the degree of relatedness to the intervention will be assessed on a 5-point scale. This approach has been used in our previous study and frequently in other studies⁵⁸⁻⁶⁰. Regarding feasibility, we will calculate the percentage of participants who a) met the inclusion criteria, b) agreed to be randomly assigned, c) completed the full tDCS+MBI protocol, and d) attended the follow-up assessment.

6.3 Treatment conditions:

The Food and Drug Administration (FDA) has ruled that the aforementioned tDCS stimulator is a "non-significant risk" device, a requirement for Investigational Device Exceptions. For pain treatment, tDCS is typically delivered

PROTOCOL TITLE:

with the anode electrode placed over the primary motor cortex (M1) and with the cathode electrode placed over the supraorbital region (SO)^{36,37}. A panel of experts from the European Chapter of the International Federation of Clinical Neurophysiology recommends 20-minute M1-SO stimulation using 2 mA electrical current intensity for possible efficacy among populations with chronic pain³⁸. tDCS with a constant current intensity of 2 mA will be applied for 20 minutes per session twice a day for 2.5 days before surgery (preop tDCS) via the Soterix 1x1 tDCS mini-CT Stimulator device (Soterix Medical Inc., NY; 6.5 inches long, 3 inches wide, 0.7 inches thick) with headgear and 5x7 cm saline-soaked surface sponge electrodes. The sponge electrodes snap into the custom headgear, which is secured to the participant's head for simple and fail-safe electrode preparation. This single-position headgear with clearly labeled sponge markers eliminates room for user error and helps conserve the placement of the montage. Participants can only administer a stimulation session via the Soterix 1x1 tDCS mini-CT Stimulator device after being provided a single-use unlock code by the research staff once proper contact quality is achieved (only the on/off button is adjustable by the study participants; they will not be able to adjust the device settings). After the participant enters the unlock code, the screen on the device will show a timer that counts down the minutes until the end of the session. At 20 minutes, the device will turn off automatically, and study staff will instruct the participant to remove the headset and discard the sponges and to safely store all materials for the next session.

For preoperative sham stimulation, the electrodes will also be placed twice a day for 2.5 days in the same positions as for active stimulation, but the stimulator will only deliver 2 mA current for 30 seconds. This sham stimulation method has been shown to be reliable and indistinguishable from active treatment^{39,40}. Regarding sham brief MBI, participants will be invited to practice a standard relaxation exercise for 3 minutes by listening to an audio recording.

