1.0 Study Summary

Study Title	Feasibility, acceptability, and preliminary efficacy of combined transcranial direct current stimulation and mindfulness for pain after total knee arthroplasty
Study Design	Pilot randomized controlled trial
Primary Objective	Assess feasibility/acceptability of the intervention
Secondary Objective(s)	Assess preliminary effectiveness on pain intensity and pain interference with activities
Research Intervention(s)/Investigational Agent(s)	Combined Mindfulness-based intervention (MBI) + transcranial direct current stimulation (tDCS) vs sham MBI+sham tDCS
IND/IDE #	
Study Population	Preoperative patients undergoing total knee replacement (TKR)
Sample Size	40
Study Duration for individual participants	1 month
Study Specific Abbreviations/Definitions	CSPS: chronic post-surgical pain MBI: mindfulness-based intervention tDCS: transcranial direct current stimulation EG: experimental group CG: control group

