4.0 Study Endpoints*

- 4.1 Measures will be taken by a research assistant via a telephone interview using a Qualtrics® survey. Outcome measures will be taken at 4 time points: 1) baseline (before preoperative active/sham tDCS+MBI), 2) after 5 sessions of preoperative active/sham tDCS+MBI, 3) after surgery, and 4) 1 month after surgery (see table below)
- 4.2 Primary endpoint: Analgesic consumption. The dose of every opioid received within 5 days postoperatively will be transcribed and converted into standardized parenteral morphine equivalents using the Centers for Disease and Control Prevention Guidelines on opioids⁴². A total in milligrams will be calculated for each day and means will be obtained for all groups.
- 4.3 Secondary endpoints: pain severity (numeric rating scale 0-100), pain interference with activities (numeric rating scale 0-10), depression and anxiety (PHQ-4), pain catastrophizing (Pain Catastrophizing Scale), multimodal quantitative sensory testing (QST) including heat pain (e.g., threshold, tolerance), pressure pain threshold, punctate mechanical pain (e.g., suprathreshold ratings and temporal summation), and Conditioned Pain Modulation (CPM), acceptability and feasibility

Day/month	B	Preoperative phase	Postoperative phase
-----------	---	--------------------	---------------------

PROTOCOL TITLE:

		Day 1	Day 2	Day 3	Day 4	Day 5	Day 1	Day 2	Day 3	Month 1
Medical History Questionnaire	X									
Analgesic consumption (primary outcome)							X	X	X	X
Clinical Pain severity (secondary outcome)										
NRS	X					X			X	X
BPI	X					X			X	X
PHQ-4	X					X			X	X
PCS	X					X			X	X
Pain-related Cortical Response (secondary outcome)										
QST measures	X					X				
Acceptability and feasibility										
tDCS + MBI experience questionnaire						X				
Side effects questionnaire		X	X	X	X	X				

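### None of the ten acceptability items asks about the mindfulness exercise or the combined package, so participant-rated acceptability of either is not directly measured

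*Protocol*

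**What the plan says.** - **Objective.** Protocol section 1.0 gives the primary objective as "Assess feasibility/acceptability of the intervention" and defines the comparison as "Combined Mindfulness-based intervention (MBI) + transcranial direct current stimulation (tDCS) vs sham MBI+sham tDCS". The acceptability objective therefore attaches to the package.
- **Session content.** Section 5.1: "Each session will start with tDCS and end with a brief mindfulness meditation using audio recording". Under section 6.3 the control arm hears a standard relaxation recording of the same 3-minute length.
- **Questionnaire as described.** Section 6.2: "We will collect data on participants' tDCS experience via a questionnaire, at the conclusion of tDCS treatment". Ten items follow, each rated for agreement from 0 to 10. Item 9 reads "The effectiveness of the treatment increased over the course of treatment" and item 10 reads "Overall, I felt that transcranial electrical stimulation treatment benefited me".
- **Questionnaire as scheduled.** The table in section 4.0 calls it the "tDCS + MBI experience questionnaire" and places it once, at preoperative Day 5.
- **Other relevant data.** Section 6.2 counts participants who "completed the full tDCS+MBI protocol" under feasibility and records side effects after every session, beginning with open questions. Section 19.1 mentions individual interviews about the intervention and how convenient it is; section 15.2 also mentions interviews.
- **Endpoint status.** Section 4.2 names analgesic consumption as the primary endpoint; section 4.3 puts acceptability and feasibility last among the secondary endpoints.
- **SAP.** It gives no analysis specific to acceptability or feasibility.

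**The concern.** The instrument's name in the schedule and its content in section 6.2 do not match. The name promises ratings of stimulation and mindfulness together; the lead-in and the items deal with stimulation and its equipment. If the plan is followed as written, a participant who found the stimulator easy to use but disliked the recording, or found the two together tiresome, has no questionnaire item on which to say so.

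What is at stake is the headline conclusion. The trial's title and primary objective invite a statement that the combined intervention is acceptable. High scores on these ten items would support such a statement for the stimulator and its remote supervision, but not directly for the mindfulness exercise or the combination. A later trial that keeps the combination on the strength of this pilot would be relying on ratings that participants were never asked to give.

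**Working it through.** No sample size, power or error rate is involved. The check is a count of the ten items in section 6.2 by what each refers to, followed by a look at every other source that might fill the gap.

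**Step 1: classify the items.**

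| Refers to | Items | Count |
|---|---|---|
| The device (preparation, complexity, ease, learning, confidence) | 1, 2, 3, 5, 6, 7, 8 | 7 |
| The video conferences | 4 | 1 |
| An unspecified treatment | 9 | 1 |
| Electrical stimulation | 10 | 1 |
| Total | | 7 + 1 + 1 + 1 = 10 |

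Items naming mindfulness, meditation, breathing, relaxation or the audio recording: 0 of 10. Items that could be read as covering the package: at most 1 of 10 (item 9).

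**Step 2: can item 9 carry the package?** It asks whether perceived effectiveness rose over the sessions. That is a judgement about effect, not about willingness, ease or burden, and an answer cannot be assigned to the recording or to the combination. Item 10, the natural place for an overall judgement, names stimulation only.

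**Step 3: do the other sources close the gap?**

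| Source | What it covers | Limit |
|---|---|---|
| Completion of the full tDCS+MBI protocol (6.2) | The package, as behaviour | Classed as feasibility; sessions are supervised live (18.0), so completion need not mean that participants liked what they did |
| Session side effects (6.2) | Treatment as a whole, with open questions first | Measures tolerability; several prompts, such as tingling, itching, burning and pain at the electrode site, are specific to stimulation |
| Interviews (19.1, 15.2) | The intervention and its convenience | No guide, timing or analysis; absent from section 6.2, the schedule and the SAP |

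Each source bears on the package. None is a specified, direct rating of the recording or of the combination.

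**Step 4: set the two descriptions of the instrument side by side.** Section 4.0 names stimulation and mindfulness; section 6.2 says stimulation experience and lists items to match. Either mindfulness items were intended and not written down, or the schedule's name is too broad. The documents do not say which.

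**The case against.** The strongest reply is that the package is not unobserved. Completion is defined for the full combined protocol. Side effects are collected at the end of each session, after the recording has been played, and prompts such as fatigue, nervousness and mood change are not confined to stimulation. Interviews are said to address the intervention itself. This stands, and it rules out a reading that one might be tempted to make: that the trial cannot assess acceptability of the combination at all. It has indirect evidence; what it lacks is a direct rating.

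A second reply is that the objective concerns the intervention as a whole, so failing to separate its components is no failure against the plan. That is fair as far as it goes. But the combination is not rated directly either, because the overall-benefit item is limited to stimulation.

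A third is proportion. A reader might infer that half of the intervention goes unmeasured. By session time the recording is 3 of 20 + 3 = 23 minutes, about 13%, and the device carries most of the practical burden, which explains the focus of the items. So the documents do not support calling it half. Still, the recording is a named component of the title and the objective, and time share does not make it dispensable.

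Finally, the administered form is not reproduced in full and may hold items that section 6.2 omits. The documents therefore support a mismatch that needs reconciling, not certainty that no such data were collected.

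**Conclusion.** The point holds in this form: of the ten listed items, none asks about the mindfulness or relaxation recording and at most one could be read as covering the package, so participant-rated acceptability of the mindfulness component and of the combination is not directly measured. The remaining evidence is indirect (completion, session side effects, item 9) or unspecified (interviews).

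This rests on two assumptions: that section 6.2 lists the whole questionnaire, and that the interviews were not run to a plan kept elsewhere. If either is wrong, the gap narrows, and documenting the fact would be enough.

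The weight is moderate. Acceptability is the primary objective in the Summary but a secondary endpoint in section 4.3, so it should not be presented as the trial's undisputed primary outcome. Under either label, the gap changes what the trial may conclude about the combination from its questionnaire.

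**What to change.** **If data can still be collected.** Add two or three 0-10 items to the existing questionnaire at the same time point, worded so that they suit both the mindfulness and the relaxation recording and do not reveal the arm. For example: the audio exercise was easy to follow; it was acceptable or helpful; I would be willing to use the stimulation and audio exercise together again. Report them by arm. The cost is a minute or two per participant and a minor amendment.

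**If collection is complete**, as the SAP's October 2025 date and past tense suggest, new items cannot help this trial. Limit the questionnaire-based acceptability conclusion to the device and tDCS. Report completion of the full protocol, session side effects and any interview data alongside it, labelled as indirect evidence on the combination. This costs wording only.

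**In either case**, reconcile the instrument's name in the section 4.0 schedule with its description in section 6.2. State whether the interviews in section 19.1 took place and, if so, give their guide, timing and analysis. If mindfulness items were in fact administered, document and report them.

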15.0 Risks to Subjects*

15.1 No adverse events have been reported in relation to mindfulness-based intervention or tDCS. We have conducted several studies on tDCS and patients minimal side effects such as slight itching (present in 30% of people as reported by systematic reviews) or tingling on the scalp (present in 70% of people as reported in systematic reviews). Although we have not observed other side effects. Systematic reviews report the possibility of dizziness in 10% of people, nausea in 3% and headache in 11% of people. The Food and Drug Administration (FDA) has ruled that the aforementioned tDCS stimulator is a “non-significant risk” device, a requirement for Investigational Device Exceptions.

15.2 Patients may feel tired while completing questionnaires, but they can pause and resume at any time. Individual interviews and some items from questionnaires may allow emotions related to the experience of a major surgery to emerge. If psychological distress becomes obvious (verbatim or score on a questionnaire), the provider will be informed for follow-up and the patient will be encouraged to communicate with the clinic.

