18.0 Provisions to Monitor the Data to Ensure the Safety of Subjects*

PROTOCOL TITLE:

[name] has the primary responsibility for monitoring study research staff. Research team will receive training on the study design, recruitment and protocol. Weekly meetings will take place with study staff to ensure protocol adherence and monthly meetings with co-investigators to discuss any issues. Patients' experiences and any potential adverse events will be reviewed and discussed. Each treatment session will be remotely supervised via zoom and after each session any potential side effects will be investigated and documented by the research coordinator (see questionnaires), [name]. This monitoring will be continued after surgery for the remainder of the data collection (up to 1 month).

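### Side effects are rated only after sessions, so within-arm rates of non-specific symptoms may include symptoms present before stimulation

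*Protocol*

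**What the plan says.** Three places in the protocol set the timing, and they agree.

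- Section 6.2 (acceptability and feasibility): "we will evaluate the presence and severity of possible side effects of treatment at the end of each session", on a 0 to 10 scale. An open question comes first, in which "the participants will be asked whether they experienced any side effects". Ten named symptoms are then prompted. Besides tingling, itching and burning, these are "pain at the stimulation site, fatigue, nervousness, headache, difficulty concentrating, mood change, and changes in vision or visual perception".
- Section 4.0, schedule table: the row "Side effects questionnaire" is marked under preoperative Days 1 to 5, and its baseline column is empty.
- Section 18.0: "after each session any potential side effects will be investigated and documented by the research coordinator".

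Section 6.2 adds an attribution step: "If any side effects are reported, the degree of relatedness to the intervention will be assessed on a 5-point scale". It does not say who makes the rating, what the five levels mean, or whether the rating affects how side effects are tabulated. The SAP does not mention side effects.

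**The concern.** Several of the prompted items are not specific to stimulation. Someone with a painful knee a few days before major surgery may already be tired, have a headache or find it hard to concentrate. Without a reading of the same items before the first session, a post-session score cannot be separated into what was there before and what is new. Whoever rates relatedness must rely on recall or judgement.

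The schedule makes the gap stand out. NRS, BPI, PHQ-4, PCS and QST are all marked at baseline; the side-effects form is the repeated symptom measure that is not.

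What is at stake is the reading of the absolute side-effect rates in each arm. The Study Summary makes feasibility and acceptability the primary objective, and the schedule places this form under that heading. Sections 4.2 and 4.3 instead make analgesic consumption primary and list acceptability among the secondary endpoints. No threshold or progression rule depends on the side-effect rates.

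**Working it through.** **Which items are affected.** Tingling, itching, burning and pain at the electrode site have little plausible background. Nervousness and mood are partly covered by the PHQ-4, which is taken at baseline and after the five sessions, though on a different scale. Mood change also asks about a change rather than a level. Fatigue, headache and difficulty concentrating have no baseline counterpart among the measures described.

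**Size, by illustration.** The documents give no figure for this point, so there is nothing to reproduce.

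Inputs:
- n = 20 per arm: 40 completers (section 12.1) at 1:1 allocation (section 6.1).
- t = 0.11: section 15.1 cites systematic reviews for "headache in 11% of people". It is treated here as the rate newly caused by active stimulation.
- b = background prevalence: not in the documents; assumed to be 0.10, 0.20, 0.30 or 0.40.
- Further assumptions: background and new headaches are independent, sham adds none, every background headache is reported, and relatedness is ignored.

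Formulas:
- Raw active-arm rate: o = 1 − (1 − b)(1 − t). Raw sham-arm rate: b.
- Share of active-arm reporters who already had the symptom: b/o.
- Expected difference between arms: o − b = t(1 − b).
- 95% half-width: 1.96 × √[o(1 − o)/20 + b(1 − b)/20].

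For b = 0.20: o = 1 − 0.80 × 0.89 = 0.288; o/t = 2.6; b/o = 0.69; o − b = 0.088; half-width = 1.96 × √(0.01025 + 0.00800) = 0.265.

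| b | Background cases per arm | Raw active rate | Ratio to 11% | Share already present | Difference (points) | 95% half-width (points) |
|---|---|---|---|---|---|---|
| 10% | 2 | 19.9% | 1.8 | 50% | 9.9 | 21.9 |
| 20% | 4 | 28.8% | 2.6 | 69% | 8.8 | 26.5 |
| 30% | 6 | 37.7% | 3.4 | 80% | 7.7 | 29.2 |
| 40% | 8 | 46.6% | 4.2 | 86% | 6.6 | 30.6 |

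Power to detect these differences runs from about 14% (b = 10%) down to 6% (b = 40%).

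**What a perfect baseline would achieve.** If all background could be removed, the comparison would be 11% against 0%. The half-width would be 1.96 × √(0.11 × 0.89/20) = 0.137, about 14 points. That is narrower than 22 to 31 points but still wider than the 11-point effect. The gain from a baseline is mainly in interpreting within-arm rates; it does not make the comparison between arms precise.

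**The case against.** A reader might infer that every pre-existing symptom is counted as a treatment side effect, or that any non-zero score is one. The documents do not say so. Participants are asked about side effects, not about symptoms in general, and reported effects are then rated for relatedness. No text states that raw scores are what will be tabulated. The questionnaire that section 18.0 points to is not reproduced, so its wording may limit answers to the session itself. The content of the baseline Medical History Questionnaire is not shown either. This argument stands: the protocol supports only the statement that pre-existing symptoms may be included.

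A reader might also infer that the comparison between arms is biased. It is not. Randomization spreads background symptoms over both arms, which are rated on the same schedule under blinding. Imprecision remains, as in any pilot of this size. Sham also delivers 2 mA for 30 seconds (section 6.3), so it is not a pure no-stimulation background, and no text commits to reporting side effects as a difference between arms.

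The inflation figures are open to challenge too. The background range is assumed, and section 15.1 does not say that its 11% is net of background. If that figure is already a raw post-session rate, adding background counts it twice. The ratios in the table are therefore not a prediction for this trial.

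Finally, section 6.2 says the approach was used in the team's previous study and is common elsewhere. That explains the choice but does not supply the missing reading.

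**Conclusion.** The concern holds in a limited form. The side-effect items have no pre-stimulation rating, so within-arm rates and severities of fatigue, headache and difficulty concentrating, and to a lesser degree nervousness and mood, may include pre-existing symptoms. The relatedness rating has no baseline value behind it, and nothing says how it enters the reporting.

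The active-versus-sham comparison is unbiased in expectation. At about 20 per arm, with half-widths of roughly 22 to 31 points under the assumed backgrounds, it is too imprecise to recover an emergent rate near 11%. The absence of a baseline reading is read directly from the protocol; the size of any inflation depends wholly on an assumed background prevalence and on taking the 11% as net of background. This is an inexpensive improvement to the acceptability evidence and does not affect the efficacy analyses.

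**What to change.** If participants are still being enrolled:

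- Add the same ten-item 0 to 10 checklist at the T-6 laboratory visit, before the first session, with one mark in the baseline column of the section 4.0 schedule.
- Report by arm the number of participants with new or worsened symptoms and the change in severity from baseline. Show raw counts and counts by relatedness level beside them.
- Define the five relatedness levels, say who assigns them, and state how they are used in the tabulation.

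The cost is a few minutes per participant at a visit already planned at about 2 hours, plus a short addition to the text. There is a statistical downside. A single T-6 reading may not match the patient's state at sessions on T-5 to T-3, so a small drift could count as worsening and a high T-6 score could hide a real effect. Showing the raw counts alongside limits that misclassification.

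The SAP is dated October 2025 and written in the past tense, so collection may be over. In that case, report side effects by arm and by relatedness level, and state that without a baseline reading the absolute rates cannot be read as treatment-emergent. This needs only tables from data already held.
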